Our goal is to create an AI-assisted diagnostic tool that can be easily integrated into clinical workflows, offering a cost-effective and accessible solution for osteoporosis screening.

• **Objectives:** The primary objective is to curate a comprehensive dataset of X-ray images sourced from publicly available domains and local health facilities, encompassing a diverse representation of patient demographics, geographic locations, and equipment variations. Building upon this dataset, we seek to develop a robust artificial intelligence model capable of prediction of bone mineral density from X-ray images.

The specific objectives of the study are:

- a) To develop a deep learning convolutional neural network (CNN) model that can accurately predict Bone Mineral Density (BMD) values from Xray images, using both prospective and retrospective data collection methods.
- b) To validate the AI model's performance on a diverse dataset encompassing a broad demographic, including variables such as age, gender, height, weight, menopausal status, and the presence of comorbidities like cardiovascular disease and diabetes.
- c) To evaluate the model's performance using a range of metrics, including Area Under the Precision-Recall Curve (AUPRC), accuracy, Mean Absolute Error (MAE), and Pearson Correlation Coefficient (PCC), ensuring its robustness in predicting BMD.
- d) To assess the usability and interpretability of the AI model's output by healthcare professionals, determining its integration into clinical practice and its impact on the diagnostic workflow efficiency.
- e) To measure the generalizability and adaptability of the model across various healthcare settings, ensuring the AI system's reliability on X-ray images from different populations and regions.

- f) To investigate the model's potential in enhancing early detection and treatment planning for osteoporosis by providing a non-invasive, cost-effective tool for BMD estimation, potentially leading to better patient management and outcomes.
- g) To assess the AI model's role as a decision support tool in determining the necessity for additional diagnostic procedures, such as DEXA scans, thereby optimizing patient care pathways and potentially reducing healthcare costs.

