 - a) **Study Population:** The study is structured as a prospective and retrospective investigation aimed at developing and evaluating an AI-based diagnostic tool for the prediction of BMD from X-ray image analysis. The population will include subjects with varying bone densities as determined by DEXA scans, which serve as the gold standard for BMD measurement. The study will target a diverse demographic to account for the variability in bone health across different ages, genders, and clinical backgrounds.

Inclusion criteria:

- Subjects of any gender and age group (18 and above) for whom X-ray imaging of relevant skeletal sites (e.g., spine, hip) is available.
- Individuals willing to participate and who have provided informed consent for the use of their X-ray images and clinical data for research purposes.
- Subjects with both X-ray images and DEXA scan results.
- Accessibility to supplementary medical records that may contribute to the model's predictive accuracy, such as historical data on fractures, calcium levels, and other osteoporosis-related factors.

Exclusion criteria:

- Subjects for whom X-ray images or clinical data are incomplete or of insufficient quality for analysis.
- Individuals with medical conditions that could significantly alter bone density independently of osteoporosis, such as bone cancers or certain metabolic diseases.
- Subjects who have undergone treatments or procedures that might significantly impact bone density measurement, such as long-term steroid use or recent orthopedic surgeries.
- Pregnant women, given the potential impact on screening results and the need for special considerations during pregnancy.
- b) **Sample size calculation:** Following the methodology of sample size calculation to evaluate diagnostic performance (for algorithms in this case), we use the following method of calculation for a target sensitivity and specificity incorporating disease prevalence [16]:

$$N_{sen} \ge \frac{Z^{2}_{(1-\alpha)/2} \times sen (1-sen)}{c^{2} \times p}$$

$$N_{spec} \ge \frac{Z^{2}_{(1-\alpha)/2} \times spec (1 - spec)}{c^{2} \times (1 - p)}$$

Where,

N _{sen}	=	Required sample size for sensitivity, sen
N_{spec}	=	Required sample size for specificity, spec
α	=	Confidence level
$Z^{2}_{(1-\alpha)/2}$	=	The Z -score for the confidence level α
p	=	Prevalence of osteoporosis
С	=	Precision
sen	_	
sen	=	Estimated sensitivity
spec	=	Estimated specificity

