The final sample size N is calculated based on the larger of the two values N_{sen} and N_{spec} . In this study, as we are using deep learning techniques, we need the medical image samples to reflect the various osteoporosis, osteopenia and normal cases. For our analysis, we assume an 95% confidence level, precision of 0.05, and prevalence of osteoporosis, p = 0.373 [8]. We estimate the sensitivity and specificity of our algorithms to be at 91.1% and 68.9% respectively (*sen* = 0.911 and *spec* = 0.689) [17]. Using these values, we obtain the sample size values: $N_{sen} = 335$ and $N_{spec} = 526$. Since $N_{spec} > N_{sen}$, the final sample size for the study will be:

$$N = N_{sen} = 526$$

We can set a target of N = 600.

c) **Procedures:** In the prospective phase of the study, data collection will be conducted within clinical settings. Eligible patients will be approached during X-ray scans and BMD tests and presented with a consent form for their consideration. Upon agreement, a unique identifier will be assigned to maintain data integrity while preserving patient anonymity. Following the consent process, patients will provide essential clinical information. Healthcare professionals will perform an X-ray or DEXA scan, and the results will be generated and collected. This approach ensures the acquisition of non-identifiable information, unique data identifiers, and informed consent directly within the clinical setting, aligning with the specific requirements of the study.

In the retrospective phase of the study, additional data will be extracted from the clinic's database. We will collect all spine and hip X-ray images and BMD reports from the radiology department. The identification and matching process will rely on patient ID, phone number, date of birth, and other shared clinical information present in both the X-ray and BMD reports. Given the retrospective nature of this approach, tracking down and obtaining consent from individual patients is not feasible. To address privacy concerns, any personally identifiable patient information will be systematically removed from the collected data. This strategy ensures compliance with privacy standards while utilizing valuable information from previous screenings. Although informed consent cannot be obtained for this specific dataset, the study will strictly adhere to ethical guidelines and prioritize patient privacy throughout the data extraction process from the clinic's database.

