- d) **Methods of Data Collection:** The following fields will be recorded in the data collection for this study:
 - Patient ID (unique identification number)
 - Date & time of the data input
 - Age
 - Gender
 - Phone number
 - X-ray image (hip or spine)

- DEXA scan result
- BMI
- Menopausal status
- Diabetes
- Cardiovascular disease and other clinical covariates

The X-ray images, and DEXA scan result of the subjects along with the relevant clinical covariates will be used to design the algorithms. The standard test status and the corresponding result will be used as the ground truth for our detection algorithm.

e) **Data Interpretation:** Upon the conclusion of data collection, exploratory data analysis to assess the distribution of patients across different demographics and clinical factors, including age, gender, menopausal status, presence of cardiovascular diseases, diabetes, and their correlation with BMD values. This process will ensure a comprehensive understanding of the dataset's characteristics and the establishment of a balanced dataset that represents a wide spectrum of patient profiles.

The refined dataset will serve as the foundation for training and evaluating our AI model, specifically designed for the regressionbased prediction of BMD from X-ray images. Our AI algorithm will leverage CNN to process X-ray images and predict BMD values, aiming to identify potential cases of osteopenia, osteoporosis, and normal.

To ascertain the model's performance and its clinical applicability, we will compare the AI-generated predictions with actual BMD measurements obtained from DEXA scans. This validation process will involve collaboration with orthopedic specialists and radiologists who will review the AI predictions in the context of their clinical experience and available patient information.

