f) Statistical Analysis: Upon finalizing the dataset, our statistical analysis will concentrate on evaluating the artificial intelligence model's capability to predict BMD from X-ray images accurately. Performance metrics such as Mean Absolute Error (MAE), Pearson Correlation Coefficient (PCC), Area Under the Precision-Recall Curve (AUPRC), and accuracy will be employed to meticulously assess the model's performance. To ensure the reliability of our findings, we will implement k-fold cross-validation techniques, providing a framework for evaluating our model across various subsets of data. This approach will allow us to calculate mean values and standard deviations for each performance metric, offering a comprehensive understanding of the model's predictive accuracy and consistency. The culmination of our analysis will involve a comparative review of different CNN architectures and training methodologies to determine the most effective strategy for BMD prediction from X-ray images.

Utilization of Results: The study results will play a crucial role in the development and evaluation of an automatic BMD prediction algorithm for osteoporosis screening. The algorithm's primary objectives are:

a) BMD Prediction: To accurately predict BMD values from X-ray images, facilitating an automated assessment tool for early detection of osteoporosis and osteopenia. This tool aims to bridge the gap in accessibility to BMD testing, especially in resource-limited settings.

b) Clinical Decision Support: To aid healthcare professionals by providing automated BMD assessments, enhancing their ability to make informed decisions regarding patient care. The model's predictions can help prioritize patients who need further testing or intervention, streamlining the diagnostic process.

c) Correlation Analysis: To explore and identify significant relationships between BMD or osteoporosis and collected clinical covariates such as age, gender, menopausal status, cardiovascular diseases, and diabetes. This analysis aims to enhance understanding of the factors influencing bone health, contributing to personalized and more precise osteoporosis risk assessment and management strategies.

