d) Data Management for Bone Health Research: To enable systematic storage and organization of X-ray images along with their corresponding BMD values and clinical data. This will not only support future research in the field of bone health but also ensure the privacy and security of patient data throughout the process.

These outcomes are poised to significantly enhance the efficiency and accuracy of osteoporosis screening, providing valuable support to healthcare professionals in Bangladesh.

- **Facilities:** For the collection of data for our thesis on predicting Bone Mineral Density (BMD) from X-ray images, no extra facilities are necessary beyond those already available in the radiology departments (e.g., X-ray imaging, DEXA scan, and data storage capabilities).
- Approval / Forwarding of the Head of Department / Institute / IRB: A forwarding letter from the Department of Biomedical Engineering, Bangladesh University of Engineering and Technology (BUET) is attached.
- **Flow Chart:** The data collection activity and the corresponding timeline is described in the Gantt chart below:

No.	Work/Activities	Months			
		1	2	3	4
1	Initial algorithm with publicly available data				
2	Collection of images, reports and metadata				
3	Homogenization and organization of data				
3	Data processing and analysis				

- Ethical Implications: The proposed retrospective/prospective study based on medical records is designed to develop and evaluate the diagnostic performance of AI algorithms that will predict BMD from X-ray images. The study poses minimal to no risk to the subjects according to the HHS (USA) definition.
- References:
 - O. Johnell and J. A. Kanis, "An estimate of the worldwide prevalence and disability associated with osteoporotic fractures," Osteoporos. Int., vol. 17, no. 12, pp. 1726–1733, Dec. 2006, doi: 10.1007/s00198-006-0172-4.
 - L. Sànchez-Riera et al., "The global burden attributable to low bone mineral density," Ann. Rheum. Dis., vol. 73, no. 9, pp. 1635–1645, Sep. 2014, doi: 10.1136/annrheumdis-2013-204320.
 - A. S. Nazrun, M. N. Tzar, S. A. Mokhtar, and I. N. Mohamed, "A systematic review of the outcomes of osteoporotic fracture patients after hospital discharge: morbidity, subsequent fractures, and mortality," Ther. Clin. Risk Manag., vol. 10, pp. 937–948, Nov. 2014, doi: 10.2147/TCRM.S72456.

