- N. Hong et al., "Deep-Learning-Based Detection of Vertebral Fracture and Osteoporosis Using Lateral Spine X-Ray Radiography," J. Bone Miner. Res., vol. 38, no. 6, pp. 887–895, Apr. 2023, doi: 10.1002/jbmr.4814.
- 15. N. Yamamoto et al., "Deep Learning for Osteoporosis Classification Using Hip Radiographs and Patient Clinical Covariates," Biomolecules, vol. 10, no. 11, p. 1534, Nov. 2020, doi: 10.3390/biom10111534.
- N. M. Buderer, "Statistical methodology: I. Incorporating the prevalence of disease into the sample size calculation for sensitivity and specificity," Acad. Emerg. Med., vol. 3, no. 9, pp. 895–900, Sep. 1996, doi: 10.1111/j.1553-2712.1996.tb03538.x.
- R. Jang, J. H. Choi, N. Kim, J. S. Chang, P. W. Yoon, and C.-H. Kim, "Prediction of osteoporosis from simple hip radiography using deep learning algorithm," Sci. Rep., vol. 11, no. 1, pp. 1–9, Oct. 2021, doi: 10.1038/s41598-021-99549-6.

Questionnaire Form

	(General In	formation		
Have you had your X-ray done at Ibn Sina, Uttara within the last 3 months?		□ (1) Yes	□ (2) No		
		If yes, what type of X-ray did you do?			
		X-ray ID	D	late	
	Ρ	articipant l	Information		
Patient ID			Date of birth		
Patient's name			Occupation		
Contact no.			Gender	□ (1) Male □ (2) Female	
Is written informed consen	; obt	tained?	\Box (1) Yes	□ (2) No	
Date of interview					
Name of interviewer					
А	nth	ropometri	c information		
Height (Feet/Inches)					
Weight (Kg/Kilogram)					
		□ (1) Yes □ (2) No			
Have you had any fractures	? 1	If yes, specify the affected area			
	(Clinical In	formation		
Menopause age					
No. of Pregnancies					
Diabetes		□ (1) Yes	□ (2) No		
Cardiovascular disease		□ (1) Yes	□ (2) No		
Parent fractured hip		□ (1) Yes	□ (2) No		
Currently smoking		□ (1) Yes	□ (2) No		
Glucocorticoids		□ (1) Yes	□ (2) No		
Rheumatoid arthritis		□ (1) Yes	□ (2) No		
Secondary osteoporosis		□ (1) Yes	□ (2) No		
Alcohol 3 or more units/day		□ (1) Yes	□ (2) No		

Project Title: Development and Evaluation of an Artificial Intelligence Model for Bone Mineral Density Prediction from X-Ray Images

JUSTIFICATIONS FOR INFORMED CONSENT WAIVER (RETROSPECTIVE STUDY)

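### No model built on archive records alone is tested on the prospective patients, so the plan cannot show how a fixed model performs on later patients

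*Protocol*

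**What the plan says.** The design has two phases. Ethical Implications puts it this way: "The proposed retrospective/prospective study based on medical records is designed to develop and evaluate the diagnostic performance of AI algorithms". Study Population states: "The study is structured as a prospective and retrospective investigation aimed at developing and evaluating an AI-based diagnostic tool". Objective (a) has the CNN developed "using both prospective and retrospective data collection methods".

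Procedures describes the phases separately. Prospective patients are approached in clinic, give consent and supply their clinical information themselves. The archive records come on top: "In the retrospective phase of the study, additional data will be extracted". These are all spine and hip X-rays and BMD reports held by radiology, matched on identifiers, without consent and with no stated time limit.

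From there on the phases are no longer distinguished. Data Interpretation says "The refined dataset will serve as the foundation for training and evaluating our AI model". Statistical Analysis says "we will implement k-fold cross-validation techniques, providing a framework for evaluating our model across various subsets of data", and then "This approach will allow us to calculate mean values and standard deviations for each performance metric". The same section closes with a comparison of CNN architectures and training methods to find the most effective one.

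Data Interpretation also has specialists review the predictions against DEXA, but sets no patients aside for this. The field list in Methods of Data Collection has a date and time of data input, but no phase.

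On timing, the Questionnaire Form asks whether the patient had an X-ray at the site "within the last 3 months".

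**The concern.** The tool is meant for patients who arrive after the model is fixed. The Rationale describes a preliminary assessment that guides whether DEXA is warranted. Objective (g) repeats that role, and objectives (b) and (e) ask for validation and generalizability.

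Cross-validation on one combined dataset answers a narrower question: how well a model does on patients drawn from the same mixture it was trained on. Two things then stay out of sight.

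- **Later patients.** If performance is lower in patients collected after the model is built, folds that mix the phases would not show it.
- **Model choice.** Architectures are compared on the same data that supply the performance figures, and no patients are kept outside that choice.

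The prospective phase could address both, because it delivers patients collected separately from the archive. The plan does not use it in this way. One mean per metric could also cover a good result in one phase and a poor one in the other.

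**Working it through.** **1. Are the phases separated anywhere in the evaluation?**

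| Stage | Protocol section | Phases kept apart? |
|---|---|---|
| Collection | Procedures | Yes |
| Recorded fields | Methods of Data Collection | No phase field |
| Training and evaluation data | Data Interpretation | No, one dataset |
| Validation scheme | Statistical Analysis | k-fold only; k and fold assignment not stated |
| Architecture comparison | Statistical Analysis | No patients set aside |
| Reporting | Statistical Analysis | Mean and SD per metric, none by phase |

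No section reserves the prospective patients, or any later period, as a test set.

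**2. What is known about timing?** The form carries a question with a 3-month limit, and Procedures gives no limit for archive X-rays. Neither is an eligibility rule, and Study Population sets no X-ray-to-DEXA interval for either phase.

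**3. The plan's own sample size.** Inputs from Sample size calculation: sensitivity 0.911, specificity 0.689, prevalence p = 0.373, precision c = 0.05, 95% confidence (z = 1.96).

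- N_sen = z² × sen × (1 − sen) / (c² × p) = 3.8416 × 0.081079 / (0.0025 × 0.373) = 334.02, rounded up to 335.
- N_spec = z² × spec × (1 − spec) / (c² × (1 − p)) = 3.8416 × 0.214279 / (0.0025 × 0.627) = 525.15, rounded up to 526.

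Both match the protocol. (Its final line labels 526 as N_sen; that is a slip for N_spec and does not affect this point.) The target of 600 covers both phases together.

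**4. Precision of a test on the prospective patients only.** The same formulas, solved for the half-width at n test patients:

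- sensitivity: 1.96 × √(0.911 × 0.089 / (0.373 × n))
- specificity: 1.96 × √(0.689 × 0.311 / (0.627 × n))

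The split by phase is not given, so every n below 600 is an assumption.

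| Prospective patients | Sensitivity half-width | Specificity half-width |
|---|---|---|
| 60 (10% of 600) | 0.118 | 0.148 |
| 100 | 0.091 | 0.115 |
| 150 | 0.075 | 0.094 |
| 200 | 0.065 | 0.081 |
| 300 (50% of 600) | 0.053 | 0.066 |
| 600 (all) | 0.037 | 0.047 |

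Even half of the target sample misses 0.05 on both measures. By step 3, a precision of 0.05 on both would need 526 patients in the test set alone.

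**5. What these numbers are.** They give the precision of the added analysis. They do not measure a bias in the planned one, which cannot be computed from the protocol. Sensitivity and specificity are used because the sample size rests on them; the metrics named in Statistical Analysis are MAE, PCC, AUPRC and accuracy.

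**The case against.** The strongest reply is that cross-validation on all available data is a recognised internal validation for a development study of about 600 patients, and that fold construction and by-phase reporting may sit in an analysis plan that is not shown. The part about fold construction stands: it is no fault of this protocol that k and the fold rule are unstated. However, the protocol does state which dataset is used for evaluation and which scheme is applied to it, and the point concerns that stated choice.

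Three stronger readings are tempting, and the documents do not support them.

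- **A reader might infer that the phases are shuffled together in one k-fold run.** Pooling follows reasonably from the single dataset, but shuffling is not mentioned. Folds formed by phase or by time are not described, nor are they ruled out.
- **A reader might infer that the phases have different X-ray-to-DEXA windows.** The 3-month item is a question on a form. It concerns the X-ray and does not mention DEXA.
- **A reader might infer that a promised prospective evaluation is missing.** None is promised. The protocol uses the two words for how data are collected, and objective (e) speaks of settings, populations and regions, not of time.

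Two further objections hold in part. The harm is not demonstrated: the archive's date range is not given, and no change in equipment or labelling is documented. Also, a comparison of the phases mixes calendar time with consent and with interview versus record-based data capture, so a drop could not be put down to time alone. It would still show how a fixed model does in patients recruited the way the prospective phase recruits them.

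**Conclusion.** The point holds as a design weakness that is cheap to repair, not as an error or a contradiction. One dataset from both phases serves training, architecture comparison and evaluation; k-fold is the only splitting scheme named; no result is planned by phase. The study as written therefore gives no estimate for a fixed model on patients who played no part in building or choosing it, although its own prospective phase could supply one.

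The conclusion assumes that the single dataset in Data Interpretation contains both phases, as objective (a) and Procedures indicate, and that no unstated fold rule separates them. The size of any optimism is unknown. What can be sized is the repair: it would be informative but imprecise, and would fall short of the planned 0.05 at any prospective share up to half of 600.

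**What to change.** Keep the pooled k-fold analysis and add three items.

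1. In Methods of Data Collection, carry a phase indicator (prospective or retrospective) into the analysis dataset. Consent status and interview date on the form should allow it to be derived, so no new question to patients is needed.
2. In Statistical Analysis, report MAE, PCC, AUPRC and accuracy by phase, from the same out-of-fold predictions as the pooled result.
3. In Statistical Analysis, add one secondary analysis: develop and choose the model on retrospective patients only, freeze it, and report all metrics on the prospective patients with 95% intervals. State that a difference between phases may reflect consent and data capture as well as time.

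The cost is analysis time: the architecture choice must be repeated on fewer patients, which is more than one extra training run. The intervals will be wide, so this should stay a secondary result. No extra patients are needed.
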